### **Clinical Laboratory Listings:**

- All clinical laboratory results: chemistry, hematology, and urinalysis
- Abnormal clinical laboratory results: chemistry, hematology, and urinalysis
- Participants with AST or ALT  $\geq 3 \times$  ULN and total bilirubin  $\geq 2 \times$  ULN, or AST or ALT  $\geq 3 \times$  ULN and INR  $> 1.5$
- Participants with Creatinine  $\geq 1.5 \times$  ULN

#### **4.6.3.4. Vital Signs**

Vital signs measurements including supine and standing systolic and diastolic blood pressure, pulse rate, respiratory rate, body temperature and weight will be taken at scheduled visit and summarized by actual received treatment across all study periods.

### **Definitions and Derivations:**

Table 8 below will be used to define the markedly abnormal vital signs.

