5.2. Exclusion Criteria

Participants are excluded from the study if any of the following criteria apply:

Medical Conditions

1. Female participants who are pregnant, nursing, or lactating or plan to become pregnant during the study or within 90 days of study completion.
2. Known history or current evidence of other medical or neurological conditions that may cause or explain the participant's tremor, in the opinion of the investigator, including, but not limited to: psychogenic tremor; myoclonus or ataxia; cerebellar disease; traumatic brain injury; alcohol abuse or withdrawal; mercury poisoning; hyperthyroidism; pheochromocytoma; multiple sclerosis; clinically significant polyneuropathy in the opinion of the investigator; or family history or diagnosis of Fragile X syndrome.

Note: Participants with a history of essential tremor are eligible.

3. Hoehn & Yahr stage 5 (confinement to bed or wheelchair unless aided).
4. Participants who only experience tremor during their "OFF" periods.
5. Severity of motor fluctuations or medication-induced dyskinesia that would interfere with the assessment of tremor and/or "ON"/"OFF" periods that are unpredictable per the opinion of the investigator.
6. Clinically significant symptomatic orthostatic hypotension in the opinion of the investigator.
7. Has evidence at Screening of cognitive impairment as defined by a MoCA score < 22 or has cognitive impairment that in the opinion of the investigator would prevent completion of study procedures or the ability to provide informed consent.
8. Received any study intervention in a previous suvecaltamide (JZP385, formerly CX8998 and MK-8998) clinical study.
9. Presence of any unstable medical or surgical history that could affect the safety of the participant or interfere with study efficacy, safety [REDACTED]; or the ability of the participant to complete the study per the judgment of the investigator. Examples of this may include, but are not limited to, untreated or currently treated malignancy or chronic infection, including human immunodeficiency virus. Note: Participants with a remote history of cancer may be eligible if the cancer has resolved and is not expected to impact safety, efficacy [REDACTED].

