### **Derivations and Definitions:**

Change from baseline to each post-baseline visit for clinical laboratory value is derived using post-baseline value – baseline value. Change from baseline to a post-baseline visit will not be derived if the laboratory assessment is missing either at baseline or at the corresponding post-baseline visit.

Values for any of the clinical laboratory parameters that are below or above the limit of quantification of the assay (BLoQ or ALoQ), will be summarized using the corresponding BLoQ or ALoQ threshold value. For listings, actual reported values will be used.

Abnormal hepatic/renal function panel values will be identified and flagged for all post-baseline visits if meeting criteria below:

- Aspartate aminotransferase (AST) or Alanine aminotransferase (ALT)  $\geq 3 \times$  Upper Limit of Normal (ULN) and total bilirubin  $\geq 2 \times$  ULN, inclusive (Hy's law)
- AST or ALT  $\geq 3 \times$  ULN and INR  $> 1.5$
- Creatinine  $\geq 1.5 \times$  ULN

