**Table 8: Markedly Abnormal Vital Signs**

Variable (unit)	Low	High
SBP (mmHg)	$\leq 90$ mmHg AND change from baseline $\leq -20$ mmHg	$\geq 180$ mmHg AND change from baseline $\geq 20$ mmHg
DBP (mmHg)	$\leq 50$ mmHg AND change from baseline $\leq -15$ mmHg	$\geq 110$ mmHg AND change from baseline $\geq 15$ mmHg
Orthostatic SBP (mmHg)	$\geq 20$ mmHg drop with posture change from supine to standing	
Orthostatic DBP (mmHg)	$\geq 10$ mmHg drop with posture change from supine to standing	
Pulse rate (bpm)	$\leq 50$ bpm AND change from baseline $\leq -15$ bpm	$\geq 120$ bpm AND change from baseline $\geq 15$ bpm
Orthostatic Pulse (bpm)	$\geq 30$ bpm drop with posture change from supine to standing	
Respiratory Rate	$\leq 12$ breaths/min	$\geq 20$ breaths/min
Weight (kg)	percentage change from baseline $\leq -10.0\%$	percentage change from baseline $\geq 10.0\%$
Temperature (°C)	$\leq 35.0$ °C	$\geq 39.0$ °C

Note: bpm = Beats per minute; DBP = Diastolic Blood Pressure; kg = kilogram; mmHg = Millimeter of mercury; SBP = Systolic Blood Pressure

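### Five rows of SAP Table 8 flag vital signs with no baseline condition, so the counts mix pre-existing with treatment-emergent findings and dilute the comparison between arms

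*SAP*

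**What the plan says.** SAP section 4.6.3.4 (Vital Signs) says that "Table 8 below will be used to define the markedly abnormal vital signs" and plans both a summary and a listing of the values so defined. The nine rows of Table 8 follow two standards:

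- **Change from baseline required.** SBP, DBP and pulse rate need an extreme level and a change from baseline. Weight is itself a percentage change from baseline.
- **No baseline condition.** Respiratory rate is flagged at 12 or below and at 20 or above. Orthostatic SBP, DBP and pulse are flagged on a supine-to-standing drop of at least 20 mmHg, 10 mmHg and 30 bpm. Temperature is flagged at 35.0 °C or below and 39.0 °C or above.

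Nothing in the section restricts the flags to post-baseline visits. The laboratory section does so for its own flags: "Abnormal hepatic/renal function panel values will be identified and flagged for all post-baseline visits if meeting criteria below". SAP section 4.1.1.3 starts the titration period for visit-based safety data, vital signs included, on the day of Baseline, so the period definition does not screen baseline readings out either.

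At entry, protocol exclusion criterion 6 removes only "Clinically significant symptomatic orthostatic hypotension in the opinion of the investigator". Protocol section 8.3.2 takes orthostatic readings in triplicate at Screening and Baseline and averages them. Later visits use a single post-dose measurement.

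**The concern.** A count of markedly abnormal values is read as a count of what happened on treatment. For SBP, DBP, pulse rate and weight that reading is safe, because a reading taken at Baseline cannot meet a change-from-baseline condition. For the other five rows it is not. A participant with an asymptomatic postural drop can be randomised and then counted in the same cell as someone whose drop first appeared on drug.

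The orthostatic rows matter most. Protocol section 2.3.1 names orthostatic hypotension among the risks to be monitored, and the SAP makes syncope an adverse event of special interest. The Table 8 count is also the only participant-level postural analysis described in the vital-signs section. The other planned summary covers supine and standing pressures and their changes from baseline. It does not name the postural difference, and mean changes do not show who newly developed a drop.

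**Working it through.** The plan gives no expected flag rate, so there is no stated figure on this point to reproduce. The only document number used is the arm size. SAP section 5 gives 64 evaluable per group, and 64 / (1 − 0.20) = 80 randomised per group, as stated. A two-sample t-test for a difference of 3.0 with SD 6.0 needs 63.8, so 64 per group, with power 80.1%. That agrees with the plan.

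**Orthostatic drop (assumed inputs).** Let q be the share already meeting the criterion at Baseline, the same in both arms by randomisation. Let c and e be the new-onset proportions on placebo and drug among the rest. If those who qualify at Baseline are counted, the flagged proportions are

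- placebo: q + (1 − q)c
- drug: q + (1 − q)e
- difference: (1 − q)(e − c)

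With c = 5% and e = 20%:

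| q | Placebo | Drug | Difference | Ratio |
|---|---|---|---|---|
| 0 | 5% | 20% | 15 points | 4.0 |
| 0.2 | 0.2 + 0.8 × 0.05 = 24% | 0.2 + 0.8 × 0.20 = 36% | 12 points | 1.5 |
| 0.4 | 0.4 + 0.6 × 0.05 = 43% | 0.4 + 0.6 × 0.20 = 52% | 9 points | 1.2 |

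With c = 10% and e = 25% the ratio falls from 2.5 to 1.4 (28% vs 40%) at q = 0.2 and 1.2 (46% vs 55%) at q = 0.4. The differences are again 15, 12 and 9 points.

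Counting new onset only, among the 80(1− q) per arm who did not qualify at Baseline, keeps the ratio at 4.0 in the first case. As a yardstick only, since safety is not tested, the power of a two-proportion comparison (5% vs 20% new onset) is 82% at q = 0. At q = 0.2 and 0.4 it is 38% and about 20% for the count as written, against 73% and 61% for new onset.

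The model counts every baseline qualifier as flagged. If fewer are flagged after Baseline, equally in both arms, the difference is unchanged and the ratio is compressed less.

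**Respiratory rate (assumed inputs, no drug effect).** Take a normal rate recorded in whole numbers. Then P(flag) = Φ((12.5 − mean)/SD) + 1 − Φ((19.5 − mean)/SD).

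- Mean 16, SD 1.5: 2 × Φ(−2.33) = 2%
- Mean 16, SD 2: 2 × Φ(−1.75) = 8%
- Mean 14, SD 3: Φ(−0.5) + 1 − Φ(1.83) = 31% + 3% = 34%

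Over means of 14 to 18 and SDs of 1.5 to 3, 2% to 34% of single readings are flagged. The protocol's Schedule of Activities gives a completer six post-baseline readings (Weeks 1, 5, 9, 13, 17 and Safety Follow-up). Simulating six readings with within-person correlation 0.3 to 0.6 gives 8% to 85% of participants flagged at least once. At mean 16, SD 2 the figure is 28% to 36%. With the limits made exclusive, that case falls to 2.4% of readings and 10% to 13% of participants, so whether 12 and 20 themselves count makes a large difference.

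**The case against.** Several points on the other side stand.

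- **Randomisation.** Both arms carry the same expected background. A reader might infer that ordinary and pre-existing values would swamp any drug signal. The documents do not support that: in the model above, the difference shrinks by the factor (1 − q) and does not vanish.
- **Other views of the signal.** Vital signs are also summarised as observed values and change from baseline, and both the values and the flagged values are listed. Protocol Appendix 4 has values that the investigator judges markedly abnormal, including worsening from baseline, recorded as adverse events. Syncope is tracked separately. All safety analysis is descriptive, so no inference depends on Table 8.
- **Persistence.** A reader might infer that a participant with a drop at Baseline is flagged at every visit. That does not follow, since Baseline is an average of three readings and later visits use one. The orthostatic criterion is also already a within-visit change, so the gap differs from that for an absolute level.
- **The respiratory limits.** A reader might infer that 12 and 20 are wrong. The documents give no respiratory-rate distribution or normal range, and nothing in them contradicts inclusive limits. The choice can be queried but not called an error.
- **Cost of a new-onset rule.** Replacing the flags with new-onset flags would hide participants whose baseline drop worsens on drug.
- **Form of the count.** The SAP does not say whether the summary counts by visit or by participant ever flagged, so the six-reading figures apply only to the latter.

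None of these answers the narrow point: for five rows, the planned count does not separate findings already present from findings that arose on treatment.

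**Conclusion.** The point holds as a small reporting gap. Table 8 uses two standards under one label without giving a reason, the section does not say that flags are post-baseline, and entry criterion 6 admits asymptomatic orthostatic drops. The resulting counts dilute the contrast between arms.

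The size is uncertain, because baseline orthostatic prevalence, new-onset rates and the respiratory-rate distribution are all assumed. On those assumptions a new-onset ratio of 4.0 could appear as 1.5 to 1.2, and 2% to 34% of single respiratory readings would be flagged with no drug effect. At the low end of the respiratory range the problem is negligible. The conclusion about the missing baseline condition rests on the text alone and does not depend on these figures. Neither the efficacy analyses nor any formal test is affected.

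**What to change.** In SAP section 4.6.3.4:

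1. State that Table 8 flags apply to post-baseline visits.
2. For the five rows without a baseline condition, report treatment-emergent flags (criterion not met at Baseline) next to the count of all flags, and keep both.
3. Add a baseline to post-baseline shift table for orthostatic blood pressure, using the averaged triplicate baseline, so that worsening of a pre-existing drop stays visible.
4. Say whether the summary counts participants by visit, ever flagged, or both.
5. Ask the sponsor to confirm that the inclusive respiratory limits of 12 and 20 are intended.

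No new data are needed. The cost is a little extra table programming, and treatment-emergent counts will be lower than the all-flags count, which should be explained in a footnote.

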**Table 8: Markedly Abnormal Vital Signs**

Variable (unit)	Low	High
SBP (mmHg)	$\leq 90$ mmHg AND change from baseline $\leq -20$ mmHg	$\geq 180$ mmHg AND change from baseline $\geq 20$ mmHg
DBP (mmHg)	$\leq 50$ mmHg AND change from baseline $\leq -15$ mmHg	$\geq 110$ mmHg AND change from baseline $\geq 15$ mmHg
Orthostatic SBP (mmHg)	$\geq 20$ mmHg drop with posture change from supine to standing	
Orthostatic DBP (mmHg)	$\geq 10$ mmHg drop with posture change from supine to standing	
Pulse rate (bpm)	$\leq 50$ bpm AND change from baseline $\leq -15$ bpm	$\geq 120$ bpm AND change from baseline $\geq 15$ bpm
Orthostatic Pulse (bpm)	$\geq 30$ bpm drop with posture change from supine to standing	
Respiratory Rate	$\leq 12$ breaths/min	$\geq 20$ breaths/min
Weight (kg)	percentage change from baseline $\leq -10.0\%$	percentage change from baseline $\geq 10.0\%$
Temperature (°C)	$\leq 35.0$ °C	$\geq 39.0$ °C

Note: bpm = Beats per minute; DBP = Diastolic Blood Pressure; kg = kilogram; mmHg = Millimeter of mercury; SBP = Systolic Blood Pressure

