8.3.2. Vital Signs

- Vital signs (to be taken prior to blood collection, when possible) including oral temperature, pulse rate, respiratory rate, and orthostatic blood pressure (systolic and diastolic) will be assessed at each clinic visit as indicated in the SoA.
- Blood pressure and pulse measurements will be assessed with a completely automated device. Manual techniques will be used only if an automated device is not available.
- Orthostatic blood pressure (systolic and diastolic) and pulse rate will be obtained after the participant has been in the supine position for at least 5 minutes, and again in the standing position after the participant has been standing for 2 minutes. At Screening and Baseline, orthostatic assessments will be taken in triplicate (at intervals of 15 to 30 minutes). All 3 measurements should be recorded. The average of the 3 measurements will be automatically calculated. At all other visits, orthostatic blood pressure and pulse assessments will consist of a single post-dose measurement.
- Respiratory rate and body temperature will be assessed after the participant has been resting and seated (or supine) for at least 5 minutes.

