### 4.1. General Considerations

Unless otherwise specified, continuous data will be summarized using descriptive statistics comprising of the number of participants with data to be summarized (n), mean, standard deviation (SD), median, minimum (min) and maximum (max). Categorical variables will be summarized as frequency and proportion.

Summaries will present the treatment groups in the following order: Placebo, JZP385.

For outputs summarized under Full Analysis Set and mITT, participants will be analyzed according to the randomized treatment arm. For outputs summarized under the Safety Analysis Set [REDACTED], to handle potential drug dispensation error(s), the actual treatment arm will be mapped according to the most frequently dispensed IMP taken by participants.

All summaries, statistical analysis, data listings, and figures will be generated using SAS version 9.4 (SAS Institute, Inc. Cary, NC) or higher. Each summary, figure, or data listing will include the data cutoff date in addition to the production date.

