### Vital Signs Summaries:

- Vital signs and change from baseline
- Markedly abnormal vital signs

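### SAP Table 8 flags orthostatic pulse only when it falls by 30 bpm or more on standing; no row flags a pulse rise on standing as a postural change

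*SAP*

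**What the plan says.** SAP 4.6.3.4 states that "Table 8 below will be used to define the markedly abnormal vital signs". The same section plans a summary and a listing of markedly abnormal values, beside a general summary headed "Vital signs and change from baseline" and a full listing.

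Table 8 has nine rows. Six (SBP, DBP, pulse rate, respiratory rate, weight, temperature) carry both a Low and a High limit. The three orthostatic rows (SBP, DBP, pulse) each carry one criterion, a drop. For pulse it is 30 "bpm drop with posture change from supine to standing". The separate Pulse rate row is High at 120 bpm or more with a change from baseline of at least +15 bpm, and Low at 50 bpm or less with a change of −15 bpm or beyond. It names no posture.

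Protocol 8.3.2 has blood pressure and pulse taken after at least 5 minutes supine and "again in the standing position after the participant has been standing for 2 minutes". SAP 4.6.3.4 describes the measurements as "supine and standing systolic and diastolic blood pressure, pulse rate, respiratory rate, body temperature and weight", which does not settle whether the posture words extend to pulse.

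**The concern.** For blood pressure, a drop-only rule fits the postural risk that Protocol 2.3.1 names, orthostatic hypotension. The pulse row repeats that wording, and neither document says why a fall is the only postural pulse change of interest. Pulse can move either way on standing, and both readings are collected, yet only one direction has a flag.

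What is at stake is how the safety output reads. A zero in the Orthostatic Pulse row could be taken to mean that nobody had a large postural change in pulse, when it means only that nobody had a large fall.

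**Working it through.** The plan states no figure to reproduce. The check applies the pulse rules in Table 8 as written.

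Inputs, all from SAP Table 8:
- Orthostatic Pulse: flag if supine − standing ≥ 30.
- Pulse rate High: flag if value ≥ 120 and value − baseline ≥ 15.
- Pulse rate Low: flag if value ≤ 50 and value − baseline ≤ −15.

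The Pulse rate row gives no posture, so it is applied here to both readings, each against the baseline in the same posture. That is the reading most favourable to the plan. The pulse values are assumed, not trial data.

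| Supine to standing (bpm) | Baseline supine/standing | Supine − standing | Orthostatic Pulse | Pulse rate row |
|---|---|---|---|---|
| 70 to 110 | any | −40 | not met | not met: 110 < 120, and neither value is ≤ 50 |
| 75 to 119 | 72/80 | −44 | not met | not met: 119 < 120 |
| 85 to 121 | 80/88 | −36 | not met | High on standing: 121 − 88 = 33 ≥ 15 |
| 85 to 121 | 80/110 | −36 | not met | not met: 121 − 110 = 11 < 15 |
| 110 to 80 | 80/85 | 30 | met | not met |
| 120 to 120 | 100/100 | 0 | not met | High: 120 − 100 = 20 ≥ 15 |

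Three things follow.

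1. For any rise, supine − standing is negative, so the Orthostatic Pulse row cannot be met whatever the size of the rise. This follows directly from the word used for the criterion. It does not depend on how the table cells were laid out.
2. To meet the row, standing pulse must be at or below supine − 30: a supine pulse of 60 needs 30 or below, 70 needs 40 or below, and 80 needs 50 or below.
3. The Pulse rate High row is not a substitute. It compares with baseline and not with the other posture. It misses the rises in the first, second and fourth lines, and it fires in the last line with no postural change. In the third line the participant is counted, if the row covers standing readings, but for absolute pulse. The Low row can likewise fire on a supine value during a rise (supine 50, supine baseline 70, change −20, standing 80), but it then reports a low pulse.

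**The case against.** The strongest reply is that no document requires a rise criterion. Orthostatic hypotension is the named postural risk, the adverse events of special interest in SAP 4.6.2 are hallucination and syncope, and Protocol 9.4.5 promises only observed and change-from-baseline summaries for vital signs. All of that is correct. What remains is an unexplained one-sided rule, which justifies asking the sponsor's medical team about direction. It does not show a copying error, and the documents do not say which direction matters clinically.

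Two stronger readings are tempting and do not hold.

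- A reader might infer that the markedly abnormal outputs cannot include anyone whose pulse rose on standing. The third line of the table shows otherwise: such a participant could appear under Pulse rate High. The supportable statement is that no row flags the rise as a postural change.
- A reader might infer that no participant-level postural difference is derived, so the general summary could never reveal a rise. The SAP does not establish this. Table 8 lists Orthostatic Pulse as a variable, and applying the row requires the supine-to-standing difference for each participant and visit. SAP 4.6.3.4 does not say whether that variable enters the general summary. If it does, the statistics in SAP 4.1 would show its mean, spread and extremes, although not a count above a limit.

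It is also fair to say that the analyses are descriptive, that the full listing keeps the readings, and that a count of rises could be produced later from data already held. These points set the level of the finding. They do not remove it, because a flag chosen after the data are seen carries less weight than one set in advance.

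**Conclusion.** The point holds as a minor one. Under Table 8 as written, a pulse rise on standing of any size never meets the Orthostatic Pulse row, and no other row identifies it as postural. The reach is the markedly abnormal vital signs summary and listing only. Raw readings, the orthostatic SBP and DBP flags, the special-interest adverse event tables and all efficacy analyses are unaffected, and nothing promised in the protocol is broken.

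The documents give no basis for estimating how many participants would be affected, so no frequency is offered; the pulse values above only illustrate the rules. The conclusion rests on the explicit direction in the Orthostatic Pulse row and on the absence of any rise criterion elsewhere in either document. The one open matter is whether the Pulse rate row covers standing readings. That changes who might appear under High, but not the conclusion.

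**What to change.** Before database lock:

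1. Ask the sponsor's medical team to confirm the intended direction of the Orthostatic Pulse criterion. Revise the row so that an increase from supine to standing is also flagged, at a threshold that the team sets, and keep the drop criterion if it was intended. If the team confirms that only a drop is of interest, state the reason in the SAP.
2. State in Table 8 whether the Pulse rate row applies to supine readings, standing readings or both.

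The cost is one table cell and one posture label in a SAP revision, with the matching programming. No new assessment is needed, because Protocol 8.3.2 already collects both readings.
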